## c) Number of Subjects

Up to 400 subjects are expected to be consented at this site. A series of 330 high risk patients undergoing elective, open or laparoscopic-assisted, clean contaminated cases involving colon resection will be enrolled in this study, of which 110 patients will receive an intraoperative application of NPWT and 220 control patients will receive the standard of care. This number was chosen based on a power analysis. Assuming the NPWT group will have a 50% reduction from the current clean-contaminated colon resection SSI rate of approximately 25%, a two-sided, chi-square power analysis indicated that with a 2:1, control to experimental ratio, 330 total subjects will be needed to detect this difference with 80% power. This number was rounded up to a

	Protocol Title:	Prophylactic Negative Pressure Wound Therapy to Reduce Surgical Site Infections in Elective Clean-Contaminated Colon Resections
	Principal Investigator	[name]
	Name/Contact Info:	[name], [contact]
Mount	Primary Contact	[name]
Sinai	Name/Contact Info	[name], [contact]
	Date Revised:	10/10/2018
	Study Number:	

total of 400 patients expected to be consented in order to account for screen failures, changes in operative and post-operative treatments, and subjects lost to follow-up. These patients will be allocated to each study arm using a simple randomization scheme. Mount Sinai performed almost 1,000 clean-contaminated colon resections in 2015, and we believe the proposed study can be completed in less than 2 years from the first enrollment.

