### d) Study Timelines

Subjects will be contacted and consented prior to surgery, and will then be followed for up to 37 days after the surgery. It is anticipated that subjects will be enrolled through June 2020. The study should be closed out between September 2020 and September 2021. An interim analysis will be conducted when approximately 50% of the subjects have completed 30 day follow-up (55 treatment; 110 control). This will allow the assumptions used to plan the study to be verified or it will allow the planned study enrollment to be adjusted.

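### Simple randomisation gives the 110/220 and 55/110 splits only in expectation and leaves balance on IBD status and surgical approach to chance; stratified blocks and an adjusted primary comparison would be a cheap improvement

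*Combined protocol and SAP*

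**What the plan says.** Section 5(c), Number of Subjects, enrols 330 patients, "of which 110 patients will receive an intraoperative application of NPWT and 220 control patients will receive the standard of care". The basis is "a two-sided, chi-square power analysis indicated that with a 2:1, control to experimental ratio", for SSI rates of 25% under control and half that under NPWT, and the section concludes that "330 total subjects will be needed to detect this difference with 80% power". The figure is raised to 400 consented patients "in order to account for screen failures, changes in operative and post-operative treatments, and subjects lost to follow-up". The allocation method follows: "These patients will be allocated to each study arm using a simple randomization scheme".

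Section 5(d), Study Timelines, places an interim analysis at about half of the completed follow-ups, written as "55 treatment; 110 control". Its purpose is to check the planning assumptions or change the enrolment target.

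Other sections bear on balance:

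- Section 5(b) admits patients through IBD, stoma reversal, reoperation within 30 days, or at least two items from a risk-factor list, and allows open or laparoscopic-assisted surgery.
- Section 9, on privacy, describes only open bowel surgery as the group approached.
- Section 5(f) places randomisation before surgery starts.
- Section 5(h) plans logistic and linear multivariate analyses, without naming covariates or linking them to the primary outcome in section 5(e).

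The document describes no blocking, stratification or minimisation, and states no allocation probability.

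**The concern.** The arm sizes are written as fixed numbers, while the named method makes them random. The interim counts have the same mismatch.

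The eligibility routes and the two surgical approaches also make it plausible that SSI risk differs within the trial. Section 2, Background, reports that the overall SSI rate has fallen but has stayed near 25% for IBD or re-operative cases. Nothing in the allocation balances IBD status or approach, and nothing commits the primary comparison to adjust for them. A visible imbalance in a single-site trial with 110 patients in its smaller arm would make the result harder to defend. At the interim it could also colour the observed rates on which an enrolment decision may rest.

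**Working it through.** **Inputs.** From section 5(c): N = 330, ratio 2:1, rates 0.25 and 0.125, two-sided chi-square, 80% power. From section 5(d): interim N = 165. Assumed because not stated: alpha 0.05, NPWT probability 1/3 per patient, exactly 330 randomised, and factor prevalence of 20% to 50%.

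**1. The plan's own figures.** 330 at 2:1 is 110/220, and half of that is 55/110. The total of 330 is close to the arcsine formula: h = 2·asin(√0.25) − 2·asin(√0.125) = 0.3245, so the NPWT arm needs (1.960 + 0.842)² × 1.5 / 0.3245² = 111.8. That gives 112 + 224 = 336, with 79.3% power at 110/220. The pooled chi-square formula gives 118 + 236 = 354, with 77.2% power at 110/220. The pooled formula is used below.

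**2. Arm size.** The NPWT count is Binomial(N, 1/3), with SD = √(N × 1/3 × 2/3).

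| | Expected | SD | 95% range | P(exact planned number) |
|---|---|---|---|---|
| End, N = 330 | 110 | 8.6 | 93 to 127 | 4.7% |
| Interim, N = 165 | 55 | 6.1 | 43 to 67 | 6.6% |

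At the end, the count lies between 100 and 120 with probability 78%. If all 400 were randomised, the expected NPWT arm would be 400/3 = 133, with a 95% range of 115 to 152.

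**3. Power.** Pooled power is Φ[(0.125 − 1.960·s0)/s1]. Here s0 is the standard error under the pooled rate and s1 the standard error under the two separate rates. At 110/220 the pooled rate is (220 × 0.25 + 110 × 0.125)/330 = 0.2083, s0 = 0.0474 and s1 = 0.0430, giving 77.2%.

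| NPWT / control | Pooled power |
|---|---|
| 93 / 237 | 72.5% |
| 110 / 220 | 77.2% |
| 127 / 203 | 80.3% |

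Averaged over the binomial distribution, power is 77.0%. The mean loss is 77.2 − 77.0 = 0.2 points. A draw of 93 or fewer has probability 2.6%.

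**4. Covariate balance.** For a factor of prevalence p, the between-arm difference has SD = √[p(1 − p)(1/n₁ + 1/n₂)]; the chance of a gap above 10 points is 2[1 − Φ(0.10/SD)].

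| p | SD, 110/220 | P(gap > 10 points) | SD, 55/110 | P(gap > 10 points) |
|---|---|---|---|---|
| 20% | 4.7 points | 3% | 6.6 points | 13% |
| 50% | 5.8 points | 9% | 8.3 points | 23% |

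These chances are per factor. At 10% prevalence the end-of-trial chance is 0.4%.

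**5. What blocking changes.** The greatest NPWT excess in an unfinished 1:2 block is 2 − 2/3 = 1.33 for size 6 and 3 − 1 = 2 for size 9. Over four strata, the total is off by at most about 5 (4 × 1.33) or 8 (4 × 2), so power stays near 77.2%.

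**The case against.** The strongest case against acting has five parts.

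- **Nothing needs exact counts.** The ratio is stated, the interim is worded as approximate, and its purpose does not depend on an exact split. This stands. A reader might infer that the plan cannot deliver its arm sizes, but the document supports only that they are not guaranteed.
- **Power is hardly affected.** This stands. A reader might blame the allocation method for power below 80%, but the pooled formula gives 77.2% at the exact planned split. That shortfall is a separate sample-size matter, and blocking does not cure it.
- **Chance imbalance is not confounding.** This stands. Randomisation keeps the comparison unbiased, and the error rate of the test already allows for chance imbalance. The effect may also be small: if a factor changed SSI risk by 10 points (an assumption), a 10-point gap would shift the difference by 0.10 × 10 = 1 point, against a target of 12.5.
- **Evidence and adjustment.** The document gives no SSI rates by IBD status or approach within the trial, so their prognostic value is a reasonable inference only. Multivariate models are planned, but with no covariates named and no tie to the primary outcome they are not yet a safeguard.
- **Blocking has a price.** The dressing is visible and section 5(b) lets the operating surgeon judge a patient unsuitable, so a predictable next assignment matters. In a block of 3, once the NPWT assignment is seen, the rest of the block is known. This is a sound reason not to rely on blocks of 3. It is weaker against larger, varied, concealed blocks.

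Blocking also fixes the numbers randomised, not the numbers analysed: losses after randomisation can still move the completed counts away from 110/220 and 55/110.

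**Conclusion.** The point holds as a cheap improvement to the design and does not threaten validity. The stated splits are expected values, with 95% ranges of 93 to 127 and 43 to 67 in the NPWT arm, and the mean power cost is about 0.2 points. Balance on IBD status and approach is left to chance. A gap above 10 points has a 3% to 9% chance per factor at the end and 13% to 23% at the interim, and the consequence is lost precision and credibility.

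These figures rest on a 1/3 allocation probability, exactly 330 randomised (165 at the interim), alpha 0.05 for the power values, and prevalences of 20% to 50%. A reader might also take simple randomisation to mean an even coin, which would give 165/165 in expectation; the explicit 2:1 ratio in section 5(c) speaks against that, but the probability should be written down.

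**What to change.** In section 5(c), replace simple randomisation with a concealed, computer-generated list of permuted blocks at 1:2 NPWT to control. Vary block size at random, for example 6 and 9, and do not rely on blocks of 3. Stratify by IBD (yes/no) and, if both approaches are enrolled, by planned approach (open or laparoscopic-assisted). Both factors should be known when randomisation takes place before surgery. Section 9 must first be reconciled with sections 5(b) and 5(c) on which approaches are eligible.

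In section 5(h), state that the primary SSI comparison is adjusted for these factors in the logistic model already planned. The planning rates imply about 220 × 0.25 + 110 × 0.125 = 69 events, so two binary covariates are no strain.

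If simple randomisation is kept, state the 1/3 probability, describe 110/220 and 55/110 as expected numbers, and still adjust the primary comparison for IBD and approach.

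The cost is one new allocation list and a few sentences. The downside is slight predictability at block ends, which varied sizes and concealment limit but do not remove.

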### d) Study Timelines

Subjects will be contacted and consented prior to surgery, and will then be followed for up to 37 days after the surgery. It is anticipated that subjects will be enrolled through June 2020. The study should be closed out between September 2020 and September 2021. An interim analysis will be conducted when approximately 50% of the subjects have completed 30 day follow-up (55 treatment; 110 control). This will allow the assumptions used to plan the study to be verified or it will allow the planned study enrollment to be adjusted.

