### Brief Summary of Research (250-400 words):

The purpose of this study is to see if the Negative Pressure Wound Therapy (NPWT) system is effective and safe for the prevention of superficial and deep incisional surgical site infections (SSI) in high risk patients within 30 days after elective colorectal surgery. It has been shown that patients with an IBD, patients undergoing a reoperation or patients with certain comorbidities are at a higher risk of developing an SSI. The NPWT device is a wound dressing with a vacuum system that can be placed over abdominal wounds. The study will include up to 400 patients at this single site, where these high risk patients will be randomized to receive either one of two arms. The first arm involves the placement of the NPWT device in the immediate postoperative period over abdominal wounds after clean-contaminated and contaminated colorectal surgical procedures. The device would then be left on for 5 days. The second arm would be standard of care and would entail routine postoperative protocols. Subjects will then be seen once at a 30 day ( $\pm$  7 days) follow-up visit to assess for the development of SSIs.

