## 3) Setting of the Human Research

Informed consent will be obtained in the offices of one of the investigators while the patient is in for an office visit or at the Mount Sinai Pre-Surgical Testing Center before the patient's screening visit. No study related tests will be performed prior to informed consent. The screening visit and surgery will take place at Mount Sinai Medical Center. The follow-up visits will take place at either the Mount Sinai Medical Center or at Mount Sinai-affiliated off-site practices. Statistical analyses will be performed on de-identified data at Mount Sinai in collaboration with the Department of Biostatistics.

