### 4) Resources Available to Conduct the Human Research

There are multiple investigators involved in this study in addition to the Principal Investigator, [name] M.D. The Principal Investigator and Co-Investigators all have extensive experience conducting research at the Mount Sinai Medical Center. Additionally, a research coordinator is employed and will be involved in the consent and data collection processes. Prior to participation, each of the investigators will have read the protocol and understand what it involves and what each of their specific responsibilities entail. The recruitment goal for this study is about 400 patients in 24 months. The investigators conduct about 83 clean/contaminated bowel resections each month. In order to meet the recruitment goal, between 15 and 20 patients would need to be consented each month. Because the vast majority of the study data-points are derived from the standard of care perioperative assessments, intraoperative clinical documentation, and the standard of care follow-up visits, meeting this screening and enrollment goal is feasible.

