## h) Data Management and Confidentiality

All research data for this study will be kept in individual patient research folders, which are locked in either a storage office on the storage of [name] or in the locked office of the research manager. In addition, data will be entered into the secure study database which will only be accessible by the research personnel. All patients will only be identified by a unique ID on all study related materials in patient research folders and on the database. The log linking ID numbers to patient identities will be kept in a password protected file on a Mount Sinai networked computer. The research manager, research coordinator, and investigators will have access to the file containing identifiers.

	Protocol Title:	Prophylactic Negative Pressure Wound Therapy to Reduce Surgical Site Infections in Elective Clean-Contaminated Colon Resections
	Principal Investigator Name/Contact Info:	[name] [name], [contact]
Mount Sinai	Primary Contact Name/Contact Info	[name] [name], [contact]
	Date Revised:	10/10/2018
	Study Number:	

The data and related publication will be stored according to MSSM's institutional guidelines. The principal investigator will keep the data on a mass storage device (example: Mount Sinai's server) for a minimum period of six years after publication. The study investigators will have access to the study data, which will be stored on a Mount Sinai secured, shared network drive. The de-identified data will be analyzed using statistical software that is installed on a secure Mount Sinai computer. Descriptive analysis and univariate tests will be performed. Logistic and linear multivariate analyses will also be run.

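### The halfway look may change enrolment without being confined to pooled data, and nothing protects the final test if N is reset from the arm difference

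*Combined protocol and SAP*

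**What the plan says.** Section 5d places the interim analysis at the point where "approximately 50% of the subjects have completed 30 day follow-up (55 treatment; 110 control"), and gives its purpose in one sentence: "This will allow the assumptions used to plan the study to be verified or it will allow the planned study enrollment to be adjusted". That is all the plan says about the look.

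The assumptions in question are in section 5c: "Assuming the NPWT group will have a 50% reduction from the current clean-contaminated colon resection SSI rate of approximately 25"%, with 80% power, a two-sided chi-square test, 2:1 allocation and a total of 330 (220 control, 110 NPWT). No significance level is stated anywhere.

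The figure 400 appears in three roles:

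- Brief Summary: "The study will include up to 400 patients at this single site".
- Section 4: "The recruitment goal for this study is about 400 patients in 24 months".
- Section 5c: "400 patients expected to be consented in order to account for screen failures, changes in operative and post-operative treatments, and subjects lost to follow-up".

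None of these ties 400 to the interim adjustment.

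On analysis, section 5h says "Descriptive analysis and univariate tests will be performed" and adds logistic and linear models; it mentions no interim adjustment. Section 3 says "Statistical analyses will be performed on de-identified data at Mount Sinai in collaboration with the Department of Biostatistics", without giving that department an interim role. Section 5h also gives the investigators access to the study data.

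**The concern.** The look is triggered by completed 30-day follow-up, and the assumptions to be checked are SSI rates, so it is almost certainly a look at the primary outcome. The control rate and the losses can be checked without comparing arms. The 50% reduction cannot. As written, the plan therefore permits a by-arm comparison followed by a change in N, without requiring one.

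If N depends on the observed arm difference, an ordinary final chi-square test no longer holds its nominal level. If N depends only on the pooled rate, it does, to a close approximation. Because the text does not fix which applies, nobody could show afterwards that the final p-value was unaffected. A rule written after the data have been seen cannot repair this.

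**Working it through.** **Inputs.** From 5c: control rate 0.25, NPWT rate 0.125, 2:1 allocation, 80% power, N = 330. From 5d: look at 110 control and 55 NPWT. Assumption: two-sided alpha 0.05.

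**1. The plan's own 330.** Pooled rate = (0.125 + 2 × 0.25)/3 = 0.2083. With the pooled-variance formula, the NPWT arm needs

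n = [1.96 √(1.5 × 0.2083 × 0.7917) + 0.8416 √(0.125 × 0.875 + 0.25 × 0.75/2)]² / 0.125² = (0.975 + 0.379)² / 0.015625 = 117.4.

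The total is 3 × 117.4 = 352.1, or 353 in whole patients (235 + 118).

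Power at 220:110: the standard error is 0.0474 under the null and 0.0430 under the alternative. (0.125 − 1.96 × 0.0474)/0.0430 = 0.746, which gives 77.2%. Exact enumeration of the chi-square test gives 77.7%.

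An arcsine formula comes closer to the plan: h = 0.3245, n = 1.5 × (1.96 + 0.8416)²/h² = 111.8, so 112 + 224 = 336, with 79.3% power at 330.

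**2. Type I error after the look.** The simulation used 1,000,000 null trials per setting, at common SSI rates of 25%, 20.8% and 12.5%, with exact 2:1 allocation. N was recomputed at 165 patients with the formula above, clipped to the stated range, and followed by an uncorrected pooled z-test at 1.96.

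| How N is reset | Range of N | Type I error |
|---|---|---|
| Fixed N | 330 | 4.9–5.1% |
| Pooled SSI rate, 50% reduction held fixed | 330–400 or 165–400 | about 4.8–5.0% |
| Control-arm rate only | 330–400 | 4.9–5.1% |
| Size of observed arm difference | 330–400 | 5.2–5.4% |
| Size of observed arm difference | 165–330 | 5.8–5.9% |
| Size of observed arm difference | 165–400 | 6.0–6.2% |

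A by-arm rule that goes to its upper limit, or keeps 330, whenever NPWT looks no better gives 5.0–5.2%, 5.4–5.5% and 5.4–5.6% over the same three ranges. The worst case over any by-arm rule, by normal approximation, is 5.4% when N can only rise from 330 to 400.

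**3. What the look could show.** Suppose it returned exactly 25% and 12.5%, that is 27.5 and 6.875 events. The standard error of the log relative risk is √(0.75/27.5 + 0.875/6.875) = 0.393. The 95% interval for the relative risk is 0.5 × exp(±1.96 × 0.393) = 0.23 to 1.08.

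The pooled rate would be 20.8 ± 6.2 points, since 1.96 × √(0.2083 × 0.7917/165) = 0.062.

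**4. N implied by the pooled rate.** With a 50% reduction, the control rate is 1.2 times the pooled rate. Pooled rates of 20.8%, 18%, 16.7% and 15% then need about 353, 422, 463 and 524 patients. The limits 14.6% and 27.0% map to about 539 and 251.

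**The case against.** The plan never says outcomes will be compared by arm. The counts 55 and 110 are expected arm sizes, not a statement that rates will be separated. Under a pooled-rate or control-rate rule there is no inflation. If N can only rise, and 400 is the ceiling, the excess is at most about 0.4 points. The 6% figures need a floor of 165, which means ending enrolment at the look, and 5d mentions no early stopping. All of this stands. It limits the size of the problem, but does not supply the missing rule.

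Four stronger readings are tempting, and the documents do not support them.

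- *The look is an unblinded efficacy test.* Two tests at 0.05, at half and full information, would give 8.3%, but the plan describes no efficacy test and no stopping rule.
- *The investigator will run the look.* The data-access wording in 5h is general, and the investigator's monitoring role in 5i concerns adverse events. Neither assigns the interim analysis.
- *400 consents yield exactly 330 enrolled, so N cannot rise.* The allowance of 70 mixes losses before and after randomisation, and no screen-failure or loss rate is given. No consent-to-enrolment rate can be derived from it.
- *The look would mainly make up for a planned N that is too small.* At the planning rates, a pooled rule asks for more than 330 in about 67% of trials. It would still ask for more than 353 in about 52%, so most of that is sampling noise.

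On 330 itself, the arcsine figure of 336 is a fair defence. The stated method is a chi-square analysis, however, and by that method the power is below 80%.

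**Conclusion.** The point holds as a gap in the design: 5d allows enrolment to change after a look that is not confined to pooled data, and no section protects the final test. The likely harm is small. Type I error is about 5.2–5.4% for a by-arm rule that only raises N to 400, and about 6% only if N may also be cut as far as stopping at the look. It is about 4.8–5.0% for a pooled rule. These figures rest on an assumed two-sided 0.05, equal true rates, exact 2:1 allocation and an uncorrected final test. The documents do not show that a by-arm rule is intended; they leave it open. The change should be made before the look, because it is cheap then and cannot be made good later.

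The separate power point also holds: about 77–78% at 330 with the chi-square test, against the stated 80%.

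**What to change.** Amend 5d to say that, at about 165 completed patients, a statistician (for example from the department named in section 3) computes only the pooled SSI rate. N is then recalculated with one named formula, holding the 50% relative reduction, 80% power and a stated two-sided alpha fixed. The minimum is 330. The maximum is stated in randomised patients and reconciled with the three uses of 400 in the Brief Summary, section 4 and 5c. State that by-arm SSI results are neither produced for nor released to investigators before the final analysis, and align the data-access wording in 5h.

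Separately, in 5c, name the sample-size formula and alpha, and restate the power of 330 or revise N.

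The cost is a few sentences and a decision on the maximum. The treatment effect is no longer checked midway, but 55 against 110 patients would estimate it only imprecisely. The pooled rate is imprecise too. With a maximum near 400, re-estimation gains nothing over a fixed 399: at 20% vs 10%, power is 73.5% with the pooled rule (330–400) and 74.2% with the fixed size. Fixing N and deleting the look is therefore a sound alternative. A higher maximum would need more patients to be consented.
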